### **4.3.2 Virology Secondary Endpoints/Estimands**

The virology endpoints/estimands are specified in [Table 1](#). Details of the analysis methods for these endpoints are listed below.

For all virology analyses, baseline is defined as the last pre-dose assessment and where no pre-dose assessment is available baseline will be defined as the first post-dose assessment on Day 1. For nasal swab influenza hemagglutinin subtype, baseline is defined as the last pre-dose assessment and where no pre-dose assessment is available, baseline will be defined as the first post-dose assessment on Days 1–3.

#### **4.3.2.1 Time to Cessation of Viral Shedding by Virus Titer**

Time to cessation of viral shedding by virus titer is defined as the time, in hours, between the initiation of study treatment and first time when the influenza virus titer was below the

lower limit of detection (LLoD). Patients whose virus titers have not reached the limit by the last observation timepoint are treated as censored at that timepoint.

Patients positive for virus titer on Day 1 will be included in the analysis.

This endpoint will be summarized using descriptive statistics by treatment, as well as Kaplan-Meier plots.

Supplementary analyses based on virus type and subtype may be conducted if there are a sufficient number of patients in each type/subtype.

#### **4.3.2.2 Time to Cessation of Viral Shedding by RT-PCR**

Time to cessation of viral shedding by RT-PCR, in hours, is defined as the time between the initiation of study treatment and the first time when the virus RNA by RT-PCR is below the LLoD (qualitative assessment). Patients whose virus RNA have not reached the limit by the last observation timepoint are treated as censored at that timepoint. For the patients with multiple virus types, this endpoint is defined as the time between the initiation of the study treatment and the first time when the virus RNA by RT-PCR qualitative result is negative for all virus types.

Patients positive for virus RNA by RT-PCR on Day 1 will be included in the analysis.

This endpoint will be summarized using descriptive statistics by treatment, as well as Kaplan-Meier plots.

Supplementary analyses based on virus type and subtype may be conducted if there are a sufficient number of patients in each type/subtype.

#### **4.3.2.3 Change from Baseline in Influenza Virus Titer at Each Timepoint**

Change from baseline in influenza virus titer ( $\log_{10}$  TCID50/mL) is defined as the change from baseline in influenza virus titer on Days 2, 4, 6, 10, 15 and 29 and will be presented by treatment. If influenza virus titer is less than the lower limit of quantification (LLoQ), the virus titer is imputed as LLoQ - 0.001 ( $0.749 \log_{10}$  TCID50/mL).

Only patients with a positive virus titer on Day 1 will be included in this analysis.

#### **4.3.2.5 Proportion of Patients with Positive Influenza Virus Titer at Each Timepoint**

Proportion of patients positive for influenza virus titer will be presented by treatment at each visit and is defined as the percentage of patients whose influenza virus titer is not less than the LLoD (0.75 log10 TCID50/mL) or is positive among those assessed for influenza virus titer on Days 2, 4, 6, 10, 15 and 29.

Patients with a positive influenza virus titer on Day 1 were included in this analysis.

#### **4.3.2.6 Proportion of Patients Positive for Virus RNA by RT-PCR at Each Timepoint**

Proportion of patients positive for virus RNA by RT-PCR will be presented by treatment at each visit and is defined as the percentage of patients with a positive qualitative result among those assessed by RT-PCR on Days 2, 4, 6, 10, 15 and 29.

Patients positive for virus RNA by RT-PCR on Day 1 will be included in this analysis.

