| Clinical laboratory tests | | 8.2.3 | | x | | | | | x | | (x ^l) | (x ^l) |
| Respiratory samples (central virology test) ⁿ | | 8.10 | x | | x | | x | | x | x | (x ^l) | (x ^l) |
| PK samples ^o | | 8.4 | | x ^p | (x) ^p | | (x) ^p | | x | | | |
| Adverse event assessment ^q | | 8.3 Appendix 3 | | x | x | (x) | x | | x | x | (x ^l) | x |

Table 1 Schedule of Activities (cont.)

BID = twice a day; CARIFS = Canadian Acute Respiratory Illness and Flu Scale; ET = Early termination; Op = optional; PCR = polymerase chain reaction; PK = pharmacokinetic; SARS-CoV-2 = severe acute respiratory syndrome–coronavirus 2; V = visit.

- ^a Informed consent/assent and screening in Index Patients can be performed on the day before Day 1.
- ^b OpV1 and OpV2 are optional visits to be performed at the discretion of the investigator or parent/caregiver, e.g., in the event of persistent influenza symptoms.
- ^c The visit may be a home visit performed by a mobile nursing professional for appropriate sites.
- ^d Can be performed remotely.
- ^e Participants will test for SARS-CoV-2 with point-of-care/local laboratory *methods*. Only participants testing PCR (–) or antigen (–) for SARS-CoV-2 will be enrolled into the study.
- ^f Oseltamivir will be given orally, 12 hours apart. If the first dose is taken after 4 p.m. (16:00 hours) on Day 1, the next dose will be taken in the morning of Day 2. For these participants, the tenth dose will be taken on the morning of study Day 6. *If the first dose is taken prior to 4 pm (16:00 hours) on Day 1, the next dose should be taken in the evening of the same day (i.e., prior to midnight on the same calendar day with a minimum of 7 hours between doses). For these participants, the tenth dose will be taken in the evening of study Day 5.*
- ^g The palatability questionnaire ([Appendix 6](#)) should be completed as soon as possible after swallowing the baloxavir marboxil drug solution on Day 1. The questionnaire will be completed for pediatric participants receiving baloxavir marboxil only.
- ^h The parent/caregiver will assess and record in the participant diary, body temperature (tympanic assessment) 4 times daily (morning, noon, evening, and bedtime) from Days 1–3; twice daily (morning and evening) on Days 4–9; once daily on Days 10–15. The results will be recorded in the participant diary.
- ⁱ On Day 1, symptom and temperature assessments for the participant diary should only be completed and filled out for the postdose time window(s).

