- ^j The parent/caregiver will complete the CARIFS questionnaire twice a day (morning and evening) on Days 1–9 and then once a day on Days 10–15. The results will be recorded in the participant diary.
- ^k A complete physical examination will be conducted at screening. Limited, symptom-directed physical examinations will be performed postdose. Height and body weight will be measured at screening only.
- ^l Conduct assessment if the investigator determines that influenza symptoms or viral shedding are persisting or at the investigator's discretion.
- ^m Vital signs will be recorded if abnormal physical examination findings or adverse events are recorded since the last visit or at the investigator's discretion on Day 29.
- ⁿ *Respiratory samples will be collected using nasopharyngeal or nasal swabs. At each swab timepoint, a virology test will be performed by the central laboratory.*
- ^o PK samples will be collected in baloxavir marboxil treated participants and sent to a central laboratory.

Table 1 Schedule of Activities (cont.)

-
- ^p PK samples will be collected at Day 1 (1 sample between 0.5 and 2 hours postdose). Participants will be assigned to have either the Day 2 (24 hours postdose) or the Day 4 sample (72 hours postdose). Only 1 sample from Days 6–10 is required and can be collected at either Visit 4 or Visit 5.
- ^q After informed consent has been obtained but prior to initiation of study treatment, only serious adverse events caused by a protocol-mandated intervention should be reported. After initiation of study treatment, all adverse events will be reported until 28 days after the first dose of study treatment. After this period, the Sponsor should be notified if the investigator becomes aware of any serious adverse event that is believed to be related to prior exposure to study drug (see [Appendix 3](#)).

Table 2 Schedule of Pharmacokinetic Samples

| Visit Day | Timepoint | Sample Type |
|--------------------|---|--------------------|
| Day 1 | One sample between 0.5 and 2 hours postdose | Drug PK (plasma) |
| Day 2 ^a | 24 hours postdose | Drug PK (plasma) |
| Day 4 ^a | 72 hours postdose | Drug PK (plasma) |
| Days 6–10 | Only 1 sample is to be collected at visit Day 6 or Day 10 | Drug PK (plasma) |

PK=pharmacokinetic.

^a Participants will be assigned to have either the Day 2 or Day 4 sample taken.

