9.3.4.6 Proportion of Participants Positive by RT-PCR at Each Timepoint

Proportion of participants positive by RT-PCR will be presented by treatment at each visit is defined as the percentage of participants with detectable virus RNA (2.05 for

influenza A and 2.83 for influenza B log₁₀ virus particles/mL) among those assessed by RT-PCR on Days 2, 4, 6, and 10.

Participants with a positive result by RT-PCR on Day 1 will be included in this analysis.

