## 1. INTRODUCTION

The analyses described in this Statistical Analysis Plan (SAP) will supersede those specified in Protocol YV44465 for the purposes of a regulatory filing.

The objective of this study is to evaluate the safety, pharmacokinetics, and efficacy of baloxavir marboxil in Chinese pediatric participants aged 1 to <12 years with influenza symptoms.

There are no changes to the planned analyses described in the protocol.

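### The SAP adds Days 15 and 29 to the by-visit virology summaries, but swabs on those days are conditional or discretionary, so the results describe a selected group

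*SAP*

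**What the plan says.** Protocol 9.3.4.6 defines percent RT-PCR positive "among those assessed by RT-PCR on Days 2, 4, 6, and 10". Protocol 9.3.4.3, 9.3.4.4 and 9.3.4.5 (change in titer, change in RNA, percent titer-positive) use the same four days.

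SAP 4.3.2.6 defines the RT-PCR proportion as the percentage with "a positive qualitative result among those assessed by RT-PCR on Days 2, 4, 6, 10, 15 and 29". SAP 4.3.2.3 takes the change in "influenza virus titer on Days 2, 4, 6, 10, 15 and 29", and 4.3.2.4 and 4.3.2.5 carry the same six days. SAP section 1 says that the SAP supersedes the protocol for a regulatory filing, and also: "There are no changes to the planned analyses described in the protocol".

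In the protocol's Schedule of Activities (Table 1), the central virology swab is unconditional at screening and on Days 2, 4, 6 and 10. On Day 15 and Day 29/ET it is bracketed and carries footnote l: "Conduct assessment if the investigator determines that influenza symptoms or viral shedding are persisting or at the investigator's discretion". Day 15 is itself an optional visit; footnote b says "OpV1 and OpV2 are optional visits to be performed at the discretion of the investigator or parent/caregiver, e.g., in the event of persistent influenza symptoms". Protocol 4.1 allows the Day 29 visit to be remote.

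SAP 4.1.1 treats a timepoint with no measurement in its window as missing. The SAP gives no fixed denominator, no rule for children who have already tested negative, and no caveat for the two late days.

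**The concern.** Up to Day 10 every child is due a swab, so the children assessed are close to the whole Day-1-positive group, apart from missed visits. After Day 10 the decision to swab depends on how the child seems to be doing. Children thought to have cleared the virus tend to leave the denominator, and those thought to be still ill or shedding tend to stay in it.

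Two misreadings could follow. Percent positive could rise after Day 10 with no change in the underlying rate. Mean change from baseline could seem to rebound, because unswabbed children who have cleared no longer contribute their large falls.

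The person deciding on the swab knows the treatment. If the threshold for swabbing differs by arm, the late columns could show a between-arm difference that comes from sampling alone. A false late signal would matter here, because protocol section 2.3 notes more treatment-emergent I38X substitutions in children than in adolescents and adults.

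**Working it through.** **Step 1. Compare the texts.**

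| By-visit summary | Protocol | SAP |
|---|---|---|
| Change in titer | 9.3.4.3: Days 2, 4, 6, 10 | 4.3.2.3: adds 15, 29 |
| Change in RNA | 9.3.4.4: Days 2, 4, 6, 10 | 4.3.2.4: adds 15, 29 |
| Percent titer-positive | 9.3.4.5: Days 2, 4, 6, 10 | 4.3.2.5: adds 15, 29 |
| Percent RT-PCR positive | 9.3.4.6: Days 2, 4, 6, 10 | 4.3.2.6: adds 15, 29 |

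The protocol's four days are exactly the post-baseline days with an unconditional swab. The two days that the SAP adds are exactly those under footnote l. The SAP's statement that nothing changed is therefore wrong for these four summaries.

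**Step 2. Size of the selection.** The documents give no Day 15 or Day 29 positivity and no swab uptake, so there is no plan figure to reproduce and the inputs below are assumptions. Let π be the true proportion positive on the day, a the chance of a swab if positive, and b the chance of a swab if negative. Then

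shown percent positive = πa / [πa + (1 − π)b].

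If a = b, this equals π. If a > b, it exceeds π. With a = 0.80:

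| True π | b = 0.20 | b = 0.10 | b = 0.05 |
|---|---|---|---|
| 2% | 0.016/0.212 = 7.5% | 0.016/0.114 = 14.0% | 0.016/0.065 = 24.6% |
| 5% | 0.040/0.230 = 17.4% | 0.040/0.135 = 29.6% | 0.040/0.0875 = 45.7% |
| 10% | 0.080/0.260 = 30.8% | 0.080/0.170 = 47.1% | 0.080/0.125 = 64.0% |

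Lowering a to 0.50 with b = 0.05 and π = 5% gives 0.025/0.0725 = 34.5%, so the result does not hinge on a high uptake among positives.

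**Step 3. Numbers behind the percentages.** The planned arms are 67 and 33 (SAP 2.2). They serve here as upper limits, because only Day-1-positive children enter these summaries. The expected number swabbed is N × [πa + (1 − π)b]. At π = 5% and a = 0.80:

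- Baloxavir: 67 × 0.230 = 15.4, 67 × 0.135 = 9.0, 67 × 0.0875 = 5.9.
- Oseltamivir: 33 × 0.230 = 7.6, 33 × 0.135 = 4.5, 33 × 0.0875 = 2.9.

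With about 3 to 8 oseltamivir children swabbed, one result moves the percentage by between 1/8 = 12.5 and 1/3 = 33 points.

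**Step 4. Difference between arms from sampling alone.** Take π = 5% and a = 0.80 in both arms, with b = 0.05 in one and b = 0.10 in the other. The arms show 45.7% and 29.6%, a gap of 16.1 points where the true gap is zero.

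The effect on mean change from baseline has the same source but was not quantified. That would need assumed titer or RNA values as well.

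**The case against.** The strongest reply is that little depends on these columns. Nothing is tested, all analyses are descriptive, the primary objective is safety, and the Day 2 to 10 columns are as the protocol planned. That stands, and it limits how serious the point is.

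The denominator of children assessed is also not new, since Protocol 9.3.4.5 and 9.3.4.6 use it too. That is correct: only the added days are new. But it is the added days that make this denominator a problem, because they are the ones without a scheduled swab for everyone. The estimand tables in both documents speak of each timepoint, which gives the extra days some textual basis. It does not override the explicit days in Protocol 9.3.4.3 to 9.3.4.6, nor does it make the SAP's statement of no change accurate.

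Three stronger readings are tempting, and the documents do not support them.

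- A reader might infer that late swabs are taken only when persistence is suspected. Footnote l also allows them at the investigator's discretion, so selection could be weaker than the footnote's first condition suggests. It is still not systematic.
- A reader might infer a ten-fold overstatement, for example 4 positive of 6 swabbed (67%) in an arm with 60 Day-1 positives (4/60 = 6.7%). That needs every unswabbed child to be negative: a swab in all 4 positives and in only 2 of 56 negatives (3.6%). This is more extreme than any case in the table.
- A reader might infer a bias towards one arm. The documents give no basis for a direction; they show only that a difference in swabbing is possible.

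**Conclusion.** The point holds as a should-fix. As written, the SAP yields percent positive and mean change on Days 15 and 29 for a group selected by an unblinded investigator, under a statement that the planned analyses are unchanged.

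The size is unknown from the documents. If 80% of positive and 5% to 20% of negative children are swabbed, a true 5% shows as about 17% to 46%, a true 2% as about 8% to 25%, and a true 10% as about 31% to 64%. If positive and negative children were swabbed equally often, there would be no distortion, only small numbers.

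A reader might take this as a threat to the trial's conclusions. It is not: it affects two late columns of four descriptive secondary summaries. The Day 2 to 10 results and the primary safety analysis are untouched, and no sample size or error rate is involved.

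**What to change.** In SAP 4.3.2.3 to 4.3.2.6, restore Days 2, 4, 6 and 10 as the summary timepoints. Present Day 15 and Day 29 results as a listing, with the number of Day-1-positive children swabbed and not swabbed in each arm.

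If a proportion over all Day-1-positive children is also wanted, label it a lower bound. It counts every unswabbed child as not positive, and a child may be unswabbed for other reasons: Day 15 is optional, Day 29 may be remote, and some children will have withdrawn.

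If any Day 15 or Day 29 summary is kept, correct the statement of no changes in SAP section 1 to declare the added days, and add a caveat to the table that sampling on those days was selective.

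The cost is a few lines of SAP text and fewer table columns. No new data are needed, and the main change returns to the protocol's own definition.

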#### **4.3.2.7 Area Under the Curve in Virus Titer**

The AUC in virus titer will be presented by treatment group and will be calculated using the trapezoidal method. AUC of change from time 0 (t0) to time K (tk) is given by the formula

$$\sum_{k=1}^K \frac{(y_k + y_{k-1})(t_k - t_{k-1})}{2}$$

where  $t_k$  (hours) represents the date of the  $k^{\text{th}}$  viral titer assessment ( $k = 0, \dots, K$ ) and  $y_k$  represents the log10 value of the  $k^{\text{th}}$  viral titer assessment (TCID50/mL).

Twenty-four hours of time will be converted into one day. Patients with a positive virus titer on Day 1 will be included in this analysis. The lower limit will be defined as 0.75 log10 TCID50/mL for flu A and flu B. If a patient is infected with multiple virus types, the sum of those virus titers will be used for analysis.

Additionally, the AUC in virus titer adjusted for baseline will be presented by treatment group and will be calculated using the trapezoidal method. AUC of change from time 0 (t0) to time K (tk) is given by the formula

$$\sum_{k=1}^K \frac{(y_k + y_{k-1} - 2y_0)(t_k - t_{k-1})}{2}$$

where  $t_k$  (hours) represents the date of the  $k^{\text{th}}$  viral titer assessment ( $k = 0, \dots, K$ ) and  $y_k$  represents the  $\log_{10}$  value of the  $k^{\text{th}}$  viral titer assessment (TCID50/mL).

Twenty-four hours of time will be converted into one day. Patients with a positive virus titer on Day 1 will be included in this analysis. The lower limit will be defined as 0.75  $\log_{10}$  TCID50/mL for flu A and 0.75  $\log_{10}$  TCID50/mL for flu B (TCID50/mL). If a patient is infected with multiple virus types, the sum of those virus titers will be used for analysis.

#### **4.3.2.8 Area Under the Curve in the Amount of Virus RNA (RT-PCR)**

AUC in virus RNA (RT-PCR) will be presented by treatment group and is defined as AUC of change from baseline in the amount of virus RNA (RT-PCR). AUC unadjusted and adjusted for baseline will be calculated using the trapezoidal method similar to AUC in virus titer.

Patients positive for virus RNA by RT-PCR on Day 1 will be included in this analysis. If a patient is infected with multiple virus types, the sum of the amount of virus RNA will be used for analysis.

#### **4.3.3 Other Secondary Endpoints/Estimands**

The other secondary endpoints are specified in [Table 2](#). Details of analysis methods for these endpoints are listed below.

##### **4.3.3.1 Polymorphic and treatment-emergent amino acid substitutions in the PA gene**

Sanger sequencing of the influenza PA gene will be performed to evaluate the incidence of polymorphic (pre-dose vs. reference) and treatment-emergent (post-dose vs. pre-dose) amino acid substitutions in subjects treated with baloxavir marboxil with evaluable virus. Sequencing will be performed for samples taken at baseline (pre-dose) and at the last evaluable timepoint (RNA titer  $\geq 4 \log_{10}$  vp/mL). The frequency of baseline polymorphic substitutions will be reported in percent of total sequenced baseline samples, and the frequency of treatment-emergent substitutions will be reported in percent of total paired samples (pre-dose and post-dose sequence pairs).

Supplementary analyses based on virus type and subtype may be conducted if there are a sufficient number of patients in each type/subtype.

##### **4.3.3.2 Drug susceptibility in participants with evaluable virus**

As assessments of the drug susceptibility of the influenza virus, the 50% effective concentration (EC50) of baloxavir will be measured by the ViroSpot™ assay using baseline swab samples for participants who receive baloxavir marboxil. EC50 values will be compared with EC50 values of reference strains and the respective ratio (EC50 / EC50 reference) will be reported.

The following influenza virus vaccines strains from the 2024/25 Northern hemisphere season will be used as references:

- A/Wisconsin/67/2022 (H1N1) pdm09-like virus
- A/Massachusetts/18/2022 (H3N2)-like virus
- B/Austria/1359417/2021-like virus (B/Victoria/2/87 lineage)

Summary statistics may be provided by virus type and subtype if there are a sufficient number of patients in each type/subtype.

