Additional data from three Japanese Phase III pediatric Studies 1618T0822 (T0822), 1705T0833 (T0833), and 1813T0835 (T0835) help support the evaluation of safety, resistance, and pharmacokinetics of baloxavir marboxil in pediatric patients aged 1 to < 12 years with a consistent safety profile. Baloxavir marboxil was well-tolerated and did not have any significant safety concerns in pediatric patients < 12 years of age.

A higher incidence of treatment-emergent I38X substitutions with reduced susceptibility has been observed in children compared with adolescents and adults. However, clinical benefit for patients with an I38X substitution was comparable with those treated with oseltamivir in Study CP40563 (Baker et al. 2020). To note, influenza viruses with reduced susceptibility to antivirals are transient in immunocompetent patients, are cleared by the immune system and have no impact on clinical progression or choice of therapy for future influenza infections (Holmes et al. 2021).

Taking into account the efficacy and safety profile of baloxavir marboxil in patients, especially the pediatric population, as well as the risk mitigations measures, the benefit-risk ratio is expected to be acceptable in this study. All participants will benefit from receiving an influenza antiviral (either oseltamivir, already approved in China, or baloxavir marboxil).

More details about the known and expected benefits, risks, and reasonably expected adverse events of baloxavir marboxil may be found in the Baloxavir marboxil Investigator's Brochure.

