8.10 VIROLOGY ASSESSMENTS

8.10.1 Respiratory Sampling

Respiratory samples will be collected at the timepoints indicated in the schedule of activities (see [Table 1](#)).

At screening, 2 samples will be collected (1 for local and 1 for central laboratory analysis) by the investigator or site staff.

For local analysis, RIDT or PCR will be used to confirm the participant is positive for influenza A/B, e.g., point-of-care/local laboratory results with use of nasal aspirate, throat swab, or nasal drip/droplet (or other appropriate sample).

Respiratory samples sent to the central labs for virology testing will be *collected using nasal swabs or nasopharyngeal swabs*, and analyzed by reverse transcriptase-polymerase chain reaction [RT-PCR], 50% of the tissue culture infectious dose (TCID₅₀), phenotyping, and genotyping.

Detailed instructions for collecting respiratory samples are provided in the laboratory manual and must be followed.

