8.10.3 Drug Susceptibility

Drug susceptibility of the influenza virus, the 50% effective concentration (EC₅₀) will be evaluated by ViroSpot™ assay for participants who receive baloxavir marboxil. For participants who received oseltamivir, drug susceptibility will be measured with the NA-Star assay.

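### SAP 4.3.3.2 omits the protocol's NA-Star susceptibility testing of oseltamivir recipients and limits baloxavir EC50 to baseline swabs, while SAP section 1 declares no changes

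*SAP*

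**What the plan says.** Protocol 8.10.3 has EC50 evaluated by the ViroSpot "assay for participants who receive baloxavir marboxil". It then adds: "For participants who received oseltamivir, drug susceptibility will be measured with the NA-Star assay". It names no sampling day for either assay. Protocol 8.10.1 lists the methods applied to swabs sent to the central laboratory, ending with "phenotyping, and genotyping". Table 1 of the protocol schedules those swabs at screening and on Days 2, 4, 6 and 10, with optional ones later.

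SAP Table 2 keeps the endpoint as drug susceptibility in participants with evaluable virus, with no limit by arm or timepoint. SAP 4.3.3.2, which gives the analysis, describes a ViroSpot "assay using baseline swab samples for participants who receive baloxavir marboxil". Each EC50 is set against the EC50 "values of reference strains and the respective ratio" is reported.

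SAP 4.3.3.1, on PA substitutions in baloxavir recipients, states: "Sequencing will be performed for samples taken at baseline (pre-dose) and at the last evaluable timepoint". SAP section 1 says that the SAP supersedes the protocol for a regulatory filing, and also: "There are no changes to the planned analyses described in the protocol".

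**The concern.** The protocol commits to measuring susceptibility in both arms, and the SAP plans to report it in one. Because the SAP governs the filing and declares no change, a reader would not learn from it that the oseltamivir result had gone. PA sequencing is confined to baloxavir recipients in both documents. Without NA-Star, the SAP therefore contains no resistance result of any kind for the oseltamivir arm.

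Within the baloxavir arm, an EC50 from a baseline swab, expressed against reference strains, describes the virus the child arrived with. It says nothing about susceptibility after dosing. The objective places susceptibility beside treatment-emergent substitutions, and protocol 2.3 gives the reason for interest: "A higher incidence of treatment-emergent I38X substitutions with reduced susceptibility has been observed in children compared with adolescents and adults". A substitution found in the post-dose sample would have no in-study phenotype beside it.

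**Working it through.** This is a comparison of texts. The plan gives no figure for this endpoint. Its only sample-size probability concerns adverse events and does not enter here.

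| Item | Protocol | SAP |
|---|---|---|
| Endpoint wording | Table 4: no limit by arm or timepoint | Table 2: same |
| Baloxavir arm, assay | 8.10.3: ViroSpot EC50 | 4.3.3.2: ViroSpot EC50 |
| Baloxavir arm, timepoint | 8.10.3: none named | 4.3.3.2: baseline swabs only |
| Oseltamivir arm | 8.10.3: NA-Star | absent |
| Emergent PA substitutions (baloxavir) | 8.10.2: post-baseline against baseline | 4.3.3.1: post-dose against pre-dose, paired |
| Declared change | not applicable | section 1: none |

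**Step 1, oseltamivir arm.** The protocol sentence on NA-Star is unconditional. No SAP section mentions NA-Star or oseltamivir susceptibility. This omission is read directly from the two texts and needs no inference.

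**Step 2, timepoint in the baloxavir arm.** The SAP's limit to baseline is explicit. The protocol states no such limit, but neither does 8.10.3 promise post-dose testing. The support for post-dose testing is indirect: 8.10.1 includes phenotyping among the central analyses, and central swabs continue after dosing. What is certain is the SAP side: it plans no post-dose susceptibility result.

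**Step 3, what remains.** SAP 4.3.3.1 reports treatment-emergent substitutions as a percentage of paired samples, and SAP 4.5.4 repeats the analysis by age group. Genotypic emergence in the baloxavir arm is therefore assessed. The phenotype of the emergent virus is not.

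**Step 4, size.** All counts are upper bounds. They assume that the planned arms are filled (67 baloxavir, 33 oseltamivir), that every mandatory swab is taken and that every swab yields evaluable virus.

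- Children with no susceptibility analysis: 33 of about 100.
- Mandatory central swabs: 100 × 5 timepoints = 500.
- Swabs that SAP 4.3.3.2 can use: 67 × 1 = 67, and 67 / 500 = 13.4%.
- Extra ViroSpot runs if one post-dose sample per baloxavir child is added: at most 67 × 1 = 67.

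The 500 shows scale only. The protocol does not promise a susceptibility test on every swab.

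**The case against.** The strongest reply has five parts.

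1. *Emergent resistance is still examined.* A reader might infer from the baseline-only EC50 that the study cannot show emergent resistance. The documents do not support that. I38X is a PA substitution, and paired PA sequencing is retained. This part stands, and the gap is phenotypic only.

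2. *No comparison was planned.* A reader might infer that a between-arm comparison has been lost. The objective for this endpoint names no comparator, unlike the objective for viral shedding and titer, and each arm has its own drug-specific assay. This stands: restoring NA-Star gives a description of the oseltamivir arm.

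3. *Post-dose phenotyping was never stated.* Protocol 8.10.2 specifies post-baseline against baseline for substitutions, while 8.10.3 is silent. The list in 8.10.1 is general and cannot mean every method on every swab, since PA sequencing is confined to baloxavir recipients. The protocol also leaves technical detail to the SAP. This largely stands. It rules out saying that all evaluable post-dose results have been dropped, but the SAP's limit still goes unexplained.

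4. *Protocol section 9 contains no susceptibility analysis, so nothing planned was changed.* This stands in part. Section 9.3 presents itself as a summary of the most important endpoints, so silence there is not exclusion. Susceptibility is a listed endpoint with a named assay per arm. Leaving one arm without any planned reporting should be declared.

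5. *The stakes are modest.* Protocol 2.3 goes on to say that clinical benefit in children with I38X was comparable with oseltamivir, and that such viruses are transient in immunocompetent patients. The study is descriptive, with safety as its primary objective. This stands as a limit on weight. It does not remove the inconsistency.

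**Conclusion.** The point holds in two parts of unequal strength. The firm part is that SAP 4.3.3.2 leaves out, without declaring it, the NA-Star testing that protocol 8.10.3 plans for oseltamivir recipients. This affects at most about 33 children, and fewer once the requirement for evaluable virus is applied; the documents give no yield from which to say how many fewer. The softer part is that baloxavir EC50 is limited to baseline swabs, a limit the protocol does not state, so phenotypic change after treatment is not assessed. Calling this second part a departure from the protocol rests on reading 8.10.1 together with the swab schedule.

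The defect does not touch the primary safety analysis, the clinical efficacy endpoints or the genotypic resistance analysis. It concerns the completeness of one descriptive secondary endpoint and the accuracy of the no-changes statement. It should be corrected before database lock.

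**What to change.** In SAP 4.3.3.2:

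- Add a descriptive NA-Star susceptibility summary for oseltamivir recipients with evaluable virus.
- Report baloxavir EC50 also at the last evaluable post-dose sample already selected for sequencing under 4.3.3.1, alongside baseline, where virus permits. State how many children have a usable pair.
- Optionally, tabulate baloxavir EC50 by presence of a treatment-emergent PA substitution. The protocol does not ask for this.

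If the sponsor intends the one-arm or the baseline-only restriction, it should instead correct the no-changes sentence in SAP section 1 and justify the restriction there.

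The NA-Star summary costs SAP text and tables, since the protocol already commits to the assay. The post-dose EC50 needs additional runs of an assay already in the protocol, at most one per baloxavir child. Yield may be low, because the protocol's background reports that baloxavir lowers viral titers faster than oseltamivir. Declaring the restriction costs only a short edit to the text.
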